## **Specific Aims**

To assess in a randomized fashion the efficacy and safety of topically applied 0.25% timolol gel in promoting wound healing and improve scar cosmesis of surgical open wounds <1.5cm when compared to the standard of care (SOC) by:

1. Evaluating healing in response to treatment with 0.25% topical timolol gel versus SOC in terms of wound surface area reduction of open surgical wound;
2. Evaluating cosmetic outcomes of surgical wounds in terms of blinded physician (4D multidimensional VAS) and patient (Visual Analogue Scale, VAS) assessment at 3 and 6 months follow up;
3. Evaluating patient discomfort during the healing process by means of a patient pain VAS;
4. Determining the side effects associated to 0.25% topical timolol versus SOC; and
5. Determining costs associated to the use of 0.25% topical timolol versus SOC.

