### Case group:

- 1) Timolol 0.25% gel will be applied to wound bed immediately after surgery before dressing is applied
- 2) Starting the day after surgery: each day, the patient will cleanse the surgical site, apply 0.25% topical timolol gel (1 drop = 0.1ml for each cm^2 of wound area), and re-cover wound with clean dressing
- 3) This daily routine continues for 12 weeks' post-surgery (even if the surgical defect has completely healed in the interim)

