### SOC group:

- 1) Vaseline will be applied to wound bed immediately after surgery before dressing is applied
- 2) Starting the day after surgery: each day, the patient will cleanse the surgical site, apply Vaseline, and re-cover wound with clean dressing
- 3) This daily routine continues for 12 weeks' post-surgery (even if the surgical defect has completely healed in the interim)

Patients will be followed up at 7, 15, and 30 days' post-surgery and then at 3 and 6 months. Standardized pictures will be taken at each time point. Wound surface area assessed by histogram planimetry (11), as well as wound infection rate will be assessed by a blinded

physician at each follow up visit. Wound area tracing by histogram planimetry will be conducted exclusively on the pictures. No tracings will be put in contact with the patients' wounds. 4D multidimensional VAS by a blinded physician and patient "scar satisfaction VAS" will be recorded at the 3 and 6 months. Patient "pain perception VAS" will be recorded at each follow up visit. Patient and physician will record any side effects occurring during the study period. Total costs in USD will also be assessed in both groups. Patients with any missing data will be asked to if they have been applying the Timolol or the Vaseline regularly, the duration of their compliance, their overall satisfaction with the wound healing process, the worst pain that they can recall and when was it after the surgery, and any other comments or concerns, including any side-effects or difficulties during the study period that they may want to share with us.

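### Adherence is asked only of patients with missing data, and those patients alone get an extra side-effect prompt; ask everyone the same questions

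*Combined protocol and SAP*

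**What the plan says.** Under Study Procedures, both arms treat themselves at home. In the timolol arm, "each day, the patient will cleanse the surgical site, apply 0.25% topical timolol gel"; the control arm does the same with Vaseline. In both arms the routine lasts 12 weeks, whether or not the wound has healed (for the control arm: "This daily routine continues for 12 weeks' post-surgery").

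The paragraph after the SOC group list sets visits at days 7, 15 and 30 and at 3 and 6 months. On side effects it gives a rule for everyone: "Patient and physician will record any side effects occurring during the study period". It then adds an interview for a subset: "Patients with any missing data will be asked to if they have been applying the Timolol or the Vaseline regularly". The same sentence goes on to ask this subset about "the duration of their compliance, their overall satisfaction with the wound healing process", about "the worst pain that they can recall and when was it after the surgery", and for "any other comments or concerns, including any side-effects or difficulties during the study period that they may want to share with us".

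Specific Aims, item 4, makes side effects a between-group comparison: "Determining the side effects associated to 0.25% topical timolol versus SOC". Item 5 does the same for costs.

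**The concern.** Adherence is a main determinant of what this trial can show, because the patient gives the treatment and nobody observes it. Asking about it only where data are missing yields adherence information on a subset selected by missingness. That subset cannot stand for the patients with complete data, who will supply most of the efficacy result. If the arms do not differ, the investigators could not tell a product that does not work from one that was not used. Actual use would also inform the cost comparison in Aim 5.

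The second, smaller matter is that the subset gets one more opportunity to report side effects than everyone else. The protocol does not say how or when the general recording is carried out, or how reports that surface only in the interview are to be combined with it. Nor does it say what will be done with the recalled worst pain and overall satisfaction from the interview, which are different measures from the pain VAS at each visit and the scar satisfaction VAS at 3 and 6 months.

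**Working it through.** **1. Who is asked what.** This is settled by reading, not arithmetic.

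| Item | All patients | Patients with any missing data |
|---|---|---|
| Regular application | none described | asked |
| Duration of compliance | none described | asked |
| Side effects | recorded by patient and physician | the same, plus an open invitation |
| Pain | VAS at each visit | also recalled worst pain |
| Satisfaction | scar VAS at 3 and 6 months | also overall satisfaction with healing |

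No diary, product weighing or adherence question appears elsewhere. The one other use of the word compliance, under Monitoring and Quality Assurance, concerns compliance with the IRB-approved protocol.

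**2. Share with unknown adherence.** Biostatistical Analysis gives 38 subjects, read here as per group, and a total of 88 to allow for attrition. No attrition rate is stated. The implied figure is 88 − 2 × 38 = 12, and 12/88 = 13.6%.
- If patients with missing data number the same as this implied attrition (assumption): 76/88 = 86.4% are never asked.
- If 5% have missing data (assumption): 0.05 × 88 ≈ 4 are asked and about 95% are not.
- If 30% have missing data (assumption): 0.30 × 88 ≈ 26 are asked and about 70% are not.

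**3. Why a null result would be hard to read.** The plan assumes 85% (timolol) and 60% (control) healed by 30 days, alpha 0.05 and 80% power; sidedness is not stated. The usual pooled-variance power formula for two proportions, with d = p1 − p2, is

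power = Φ[(d − z·√(2·p̄(1 − p̄)/n)) / √(p1(1 − p1)/n + p2(1 − p2)/n)].

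With n = 38 per arm this gives 79.6% one-sided (z = 1.645), close to the stated 80%, and 69.2% two-sided (z = 1.960).

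Now suppose, as an illustration only, that a fraction f of the timolol arm does not use the gel during the first 30 days and heals at the control rate. Then p1 = 0.85(1 − f) + 0.60f.

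| f (assumed) | p1 | Power one-sided | Power two-sided |
|---|---|---|---|
| 0 | 0.850 | 79.6% | 69.2% |
| 0.10 | 0.825 | 70.5% | 58.5% |
| 0.20 | 0.800 | 60.4% | 47.6% |
| 0.30 | 0.775 | 50.0% | 37.4% |

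Measuring adherence would not restore this power. It would show whether non-use on this scale had occurred.

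**4. Size of the side-effect problem.** Assume a true rate of 20% in both arms, capture of 50% by routine recording, and capture of 90% by recording plus interview. With a proportion m missing, the observed rate is 0.20 × [0.90m + 0.50(1 − m)].
- m = 5% against 20%: 10.4% against 11.6%, a spurious difference of 1.2 points, or 0.012 × 44 ≈ 0.5 patient with 44 per arm.
- m = 10% against 30%: 10.8% against 12.4%, a difference of 1.6 points, or 0.016 × 44 ≈ 0.7 patient.
- Equal m: no difference.

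**The case against.** The strongest case against the point is that it does not touch the validity of the randomized comparison. Unmeasured adherence leaves an analysis by assigned arm unbiased; what suffers is interpretation. That stands, and it is why this is a cheap improvement and not a defect that invalidates the plan.

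On side effects, a reader might infer that ascertainment itself depends on missingness, or that patients with complete data are never covered. The text does not support this. Recording by patient and physician applies to everyone, and the interview item is an open invitation, not a structured checklist. The protocol does not describe the general recording as passive. Patients who miss visits may also lose physician recording at those visits, so the extra prompt may partly replace what was lost, and the net effect could be smaller than in the illustration or reversed. No figure in the documents predicts unequal missingness between arms.

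Two further readings are tempting and should be resisted. One is that recalled worst pain will replace missing visit scores and push pain upward. No such substitution is proposed; the intended use is simply not stated. The other is that adherence would be seen only in the least adherent patients. A missed visit or a missing score does not show that a patient stopped applying the product. The sounder statement is that a subset selected by missingness does not represent the rest.

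Finally, missing data and attrition are not the same. Any one missing item over five visits triggers the interview, which could take in many more than 12 patients, while some patients lost to follow-up could not be interviewed at all. The 86% is therefore one value in an assumed range.

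**Conclusion.** The adherence part holds from the text alone. Followed as written, the protocol collects no adherence information from patients with complete data on a daily, self-applied, 12-week treatment. The share affected is not known: about 86% if missing data match the implied 12 of 88, and about 70% to 95% if 30% to 5% have missing data. These are assumptions, but adherence is unknown in a large majority throughout the range.

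The side-effect part holds only as a difference in intensity. Patients with missing data get one additional open prompt, so the Aim 4 comparison could be distorted if missingness differs between arms. Under the assumed capture rates the distortion is 1.2 to 1.6 points, less than one patient per arm, and it is zero if missingness is equal. The documents do not support a claim that Aim 4 is seriously biased or that pain scores will be inflated. The point is worth acting on because the remedy is small, and because adherence not recorded during treatment can later be recovered only by recall.

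**What to change.** Replace the selective interview with a short set of adherence and side-effect questions, worded identically for every patient in both arms.
- **When:** adherence and side effects at the existing day 7, 15, 30 and 3-month visits; side effects also at 6 months. After a missed visit, ask the same questions by phone.
- **Who asks:** existing study staff other than the blinded assessing physician, since questions about a named product could reveal the arm.
- **Reporting:** list side effects found only through the missed-visit interview separately from those recorded routinely. If recalled worst pain and overall satisfaction are still collected, state that they are descriptive only and are not entered as visit pain VAS or scar satisfaction VAS.

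The cost is a few minutes per existing visit, one case-report-form page and a protocol wording change. It needs no new visit, no change to treatment and no larger sample.

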### **Biostatistical Analysis**

To detect a 25% difference in time to improvement in each treatment arm with an 80% power, a total of 38 subjects will be enrolled in both the treatment and SOC groups (alpha level=0.05). Total subject enrollment will be 88 to adjust for subjects lost to attrition. This was calculated by considering the percentage of patients that would be healed by 30 days. In the timolol group, we estimate 85% and in the control group we estimate 60%. The Mohs and Dermatologic Surgery Center has 3 surgeons who use second intention healing on approximately 505 cases per year (~42 cases per month). If 50% of subjects agree to participate, enrollment will be complete within approximately 5 months.

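### The 80% power is claimed for a 25% difference in time, but was calculated for a 25-percentage-point difference in day-30 healing, and no primary endpoint is named

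*Combined protocol and SAP*

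**What the plan says.** The Biostatistical Analysis section of the combined protocol and SAP is one paragraph. It opens with the effect to be detected: "To detect a 25% difference in time to improvement in each treatment arm with an 80% power". It sets the size as "a total of 38 subjects will be enrolled in both the treatment and SOC groups", at "alpha level=0.05", and adds "Total subject enrollment will be 88 to adjust for subjects lost to attrition". It then explains the derivation: "This was calculated by considering the percentage of patients that would be healed by 30 days". The rates are given as "In the timolol group, we estimate 85% and in the control group we estimate 60" per cent.

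Specific Aims, item 1, evaluates healing "in terms of wound surface area reduction of open surgical wound" and gives no timepoint. Study Procedures has area measured by blinded planimetry on photographs at days 7, 15 and 30 and at 3 and 6 months.

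No section names a primary endpoint, defines improvement or healed, states whether alpha is one- or two-sided, or specifies a test.

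**The concern.** The power sentence names a change in time. The calculation behind it compares two proportions at a fixed day. The first aim concerns a change in area. These are different quantities, and the same 25% does not carry over from one to another: a 25% shortening of healing time is generally not the same effect as moving from 60% to 85% healed at day 30.

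Two things are at stake. First, someone who takes the power sentence at face value will believe that the trial has an 80% chance of detecting a 25% gain in time, which the calculation does not show. Second, with no primary endpoint, timepoint or test fixed, the plan does not say which healing result will decide the trial. The outcome used for sizing is in no aim, and the outcome in Aim 1 has no effect size, standard deviation or power.

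**Working it through.** **Inputs.** From Biostatistical Analysis: 85% and 60% healed by day 30, power 80%, alpha 0.05, 38 subjects, 88 enrolled. The 38 is read as per arm, 76 in all, with 1:1 allocation. Used as a total (19 per arm) it would give only about 40% two-sided or 53% one-sided power.

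**1. Reproduce the plan's figure.** 0.85 − 0.60 = 0.25, so the 25% is an absolute difference in proportions. With mean proportion 0.725, the pooled two-proportion formula is

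n = [z_α √(2 × 0.725 × 0.275) + z_β √(0.85 × 0.15 + 0.60 × 0.40)]² / 0.25²

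- One-sided 0.05 (z_α = 1.645, z_β = 0.842): n = 38.4. The arcsine formula gives 37.5, which rounds up to 38.
- Two-sided 0.05 (z_α = 1.960): n = 48.9, so 49.

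Of these, only the one-sided calculation comes out at about 38. A relative 25% increase, 60% to 75%, would need 120 per arm one-sided or 152 two-sided, so that reading does not fit.

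**2. Power for 85% versus 60%.** Power = Φ{[√n × 0.25 − z_α √(2 × 0.725 × 0.275)] / √0.3675}.

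| Evaluable per arm | One-sided 0.05 | Two-sided 0.05 |
|---|---|---|
| 38 | 79.6% | 69.2% |
| 44 (all 88 enrolled) | 84.7% | 75.6% |

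**3. What a 25% shorter time would mean at day 30.** The documents give no distribution, so one must be assumed. With exponential times and 60% of controls healed at day 30, rate × 30 = −ln(0.40) = 0.916. Multiplying times by 0.75 gives 1 − exp(−0.916/0.75) = 0.705. For 70.5% versus 60% at 38 per arm, the same formula gives power of about 16% two-sided and 25% one-sided. The benchmarks are the 69% and 80% in step 2.

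The result depends on the spread of healing times. With log-normal times, the proportion healed is Φ(0.253 + 0.288/SD), where SD is the log-scale standard deviation:

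| Log-SD (assumed) | Power two-sided | Power one-sided |
|---|---|---|
| 0.5 | 46% | 59% |
| 0.7 | 27% | 39% |
| 1.0 | 16% | 25% |

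A 25% shortening gives exactly 85% only at log-SD 0.288/(1.036 − 0.253) = 0.37. With a smaller spread it would give more than 85%.

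**4. The same effect with a time-to-event test.** Under exponential times, a time ratio of 0.75 is a hazard ratio of 1/0.75 = 1.33. Events needed for 80% power, two-sided (Schoenfeld): 4 × (1.960 + 0.842)² / (ln 1.333)² ≈ 380. If all 76 subjects healed and were counted, power = Φ(√76/2 × 0.288 − 1.960) ≈ 24%. If the 25% is read as a hazard ratio of 1.25, the figures are 631 events and 16%.

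**5. The reverse direction.** Under exponential times, 85% versus 60% at day 30 is a hazard ratio of ln(0.15)/ln(0.40) = 2.07. Healing times are then 1 − 1/2.07 ≈ 52% shorter, not 25%.

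No power can be computed for Aim 1, because no effect size or standard deviation for area reduction is given.

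**The case against.** The strongest reply is that the section explains itself. It says how the number was obtained and gives both rates, and about 38 per arm follows from them. On that view the phrase about time is a mislabel and the design was not miscalculated. This stands: the sample size was not built on a time effect. What remains is that the power claim is attached to the wrong quantity and that the right one appears in no aim.

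Several stronger readings are tempting and should not be drawn:

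- **That the trial has 16% power.** That figure tests an effect the calculation did not use, under an assumed distribution. A time-to-event test would do somewhat better (24%), and at log-SD 0.37 the two effects coincide.
- **That three endpoints share one power statement.** Aim 1 has none. Area and healing are also linked, since complete healing is area zero.
- **That the error rate is inflated to a known figure.** Counting every outcome at every visit gives about 21 comparisons, and five independent tests at 0.05 would give 1 − 0.95⁵ = 23%. But no section says that each outcome is tested at 0.05. The count includes costs, infection and side effects, which are not rival healing endpoints. Repeated measures of one wound are correlated, so 23% is a loose upper bound.
- **That spaced visits rule out a time analysis.** They make healing times interval-censored, which can be handled.
- **That a one-sided test was intended.** The match to 38 suggests it, but the document does not say so.

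**Conclusion.** The point holds in this form: the stated 80% power belongs to a 25-percentage-point difference in day-30 healing and does not apply to the 25% difference in time that the sentence names. The sized outcome is in no Specific Aim, the Aim 1 outcome is unpowered and has no timepoint, and no primary endpoint is named. These statements rest on the text and on simple subtraction.

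The size of the gap is illustrative because it depends on an assumed distribution. Under exponential times, power for a 25% shortening is about 16% two-sided or 25% one-sided on the day-30 comparison. The power of about 80% for the effect actually calculated also depends on one-sided 0.05; at two-sided 0.05 it is about 69% with 38 evaluable per arm.

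**What to change.** - In Biostatistical Analysis, replace the opening of the power sentence with: *To detect a 25-percentage-point difference in the proportion completely healed by day 30 (85% vs 60%)*. Delete the reference to time to improvement.
- Under Aim 1, name complete healing by day 30, defined as blinded planimetric area of zero, as the single primary endpoint, and state the test. Make area reduction and all other outcomes secondary, reported with confidence intervals.
- State the sidedness and restate the power to match: about 80% at one-sided 0.05 or about 69% at two-sided 0.05 with 38 evaluable per arm (about 76% two-sided if all 44 per arm are evaluable).

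The planimetry and the day-30 visit are already planned, so no measurement is added. The cost is that secondary outcomes lose confirmatory status and the stated power falls if the test is two-sided. Keeping 80% at two-sided 0.05 would take 49 per arm; at the attrition implied by 76 of 88, that is 98 × 88/76 ≈ 114 enrolled instead of 88.

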## **Study Procedures**

The study protocol will begin immediately post-surgery. Eligible subjects will be assigned by computer-based randomization to case (0.25% timolol gel) or control (SOC) group and treated as follows:

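### The stated 80% power holds only for an undeclared, uncorrected one-sided 5% test; at two-sided 5%, 38 per group gives about 70%

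*Combined protocol and SAP*

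**What the plan says.** All of the sample-size reasoning is in the Biostatistical Analysis section of the combined protocol and SAP.

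- Target: "To detect a 25% difference in time to improvement in each treatment arm", "with an 80% power".
- Size: "a total of 38 subjects will be enrolled in both the treatment and SOC groups (alpha level=0.05").
- Enrolment: "Total subject enrollment will be 88 to adjust for subjects lost to attrition".
- Basis: "This was calculated by considering the percentage of patients that would be healed by 30 days".
- Planning rates: "In the timolol group, we estimate 85% and in the control group we estimate 60" (percent).

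The section does not name a test or a formula, say whether alpha is one- or two-sided, or give an attrition rate. No other section supplies these. Study Procedures describes the randomisation ("Eligible subjects will be assigned by computer-based randomization to case (0.25% timolol gel) or control (SOC) group") without an allocation ratio.

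**The concern.** The rates, alpha and power are all stated, so the sample size can be checked directly. The usual two-proportion calculation at two-sided 5% gives 49 per group, well above 38. The stated 38 appears when alpha is spent on one side only, and the plan does not say that it is.

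Two things are at stake. First, a reader who takes alpha of 0.05 in its conventional two-sided sense will believe that the risk of missing the assumed effect is 20%, when it is about 30%. A null result could then be over-read as evidence of no effect. Second, while sidedness is open, it could be settled after the data are seen. A result in favour of timolol with a two-sided p-value between 0.05 and 0.10 would be significant under one choice and not under the other.

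**Working it through.** **Inputs from the Biostatistical Analysis section.** p1 = 0.85, p2 = 0.60, difference d = 0.25, alpha = 0.05, power 80%, 38 subjects, enrolment 88.

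**Assumptions.** Allocation is 1:1 (the ratio is not stated). The 38 is per group: 2 × 38 = 76 evaluable, and 88 enrolled then allows for 12/88 = 13.6% lost. An inflation of 38 × 1.15 = 43.7, rounded to 44 per group, also gives 88.

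**Formula (pooled normal approximation).** With the mean rate p = 0.725:

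- A = √(2 × 0.725 × 0.275) = √0.39875 = 0.6315
- B = √(0.85 × 0.15 + 0.60 × 0.40) = √0.3675 = 0.6062
- n per group = (z_alpha × A + 0.8416 × B)² / d²
- power = Φ[(d√n − z_alpha × A) / B]

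**Step 1: reproduce the plan's figure, one-sided 5% (z = 1.6449).**

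- n = (1.0387 + 0.5102)² / 0.0625 = 38.4 per group
- Power at 38 = Φ[(1.5411 − 1.0387) / 0.6062] = Φ(0.829) = 79.6%

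The stated 38 and 80% reproduce to within rounding.

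**Step 2: the same calculation at two-sided 5% (z = 1.9600).**

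- n = (1.2377 + 0.5102)² / 0.0625 = 48.9, so 49 per group
- Power at 38 = Φ[(1.5411 − 1.2377) / 0.6062] = Φ(0.501) = 69.2%
- Power at 44 = Φ[(1.6583 − 1.2377) / 0.6062] = Φ(0.694) = 75.6%

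**Step 3: does the choice of method change the answer?**

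| Method | n for 80%, one-sided | n for 80%, two-sided | Power at 38, one-sided | Power at 38, two-sided | Power at 44, two-sided |
|---|---|---|---|---|---|
| Pooled normal | 39 | 49 | 79.6% | 69.2% | 75.6% |
| Unpooled normal | 37 | 47 | 81.5% | 72.0% | 78.1% |
| Arcsine | 38 | 48 | 80.4% | 70.6% | 76.8% |
| Chi-square, exact enumeration | – | – | 80.5% | 71% | 77.3% |
| Continuity-corrected normal | 47 | 57 | 71.3% | 59.2% | 67.2% |
| Fisher's exact test, exact enumeration | – | – | 73.1% | 61.9% | 68.0% |

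No two-sided method gives 38, and none reaches 80% even at 44 per group. One-sided testing reaches about 80% at 38 per group only without a continuity correction and without Fisher's test.

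**Step 4: what 38 per group can detect at two-sided 5%.** Solving the pooled formula for p1 against 60% gives 87.8%, a difference of about 28 points rather than 25.

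**Step 5: could the wording about time to improvement explain the figure?** This check assumes exponential healing times. The hazard ratio is then ln(0.15)/ln(0.40) = 2.07, and 72.5% of subjects on average heal by day 30. Schoenfeld's formula needs 60 events two-sided (60/0.725, about 83 patients) or 47 one-sided (about 65 patients). Freedman's needs 65 (about 90) or 51 (about 70). None of these gives 76.

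**The case against.** The strongest reply is that there is no arithmetic error. The 38 and the 80% agree under a standard one-sided 5% calculation, and the documents never commit to a two-sided test. The text also leans in one direction: the Specific Aims speak of promoting healing, and Potential Benefits expects faster healing with timolol. Aim 1's comparison with standard of care names a comparator and says nothing about sidedness.

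This stands, and it limits the point. A reader might infer that the stated power is simply wrong. The documents do not support that, because the figure is right under one common variant. A reader might also infer that the sponsor used a one-sided formula. That is the likeliest origin of 38, but it is deduced from the arithmetic and is not stated. Nor should the sentence be read as 38 subjects overall: the wording is loose, but an enrolment of 88 rules that reading out.

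It is also fair to say that about 70% is the power of one analysis, a comparison of proportions healed at 30 days with attrition down to 38 per group. Aim 1 is framed as surface-area reduction, and the section itself mentions time to improvement. The 30-day proportion is nevertheless the quantity on which the section says its calculation rests.

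The omission still matters. An expected direction of benefit is not a declaration of a one-sided test. Even if one were declared, 80% would not be secured until the test is named: one-sided Fisher gives 73.1% at 38 per group.

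**Conclusion.** The point holds as a failure to specify the test, with a material effect on the stated power. For 85% versus 60% healed by 30 days, 38 per group has 80% power only with an uncorrected one-sided 5% test. At two-sided 5% the power is about 70% (69% pooled, 71% exact chi-square, 62% Fisher), so the risk of missing the assumed effect is about 30%, or 38% with Fisher. With no attrition and 44 per group, power is about 76% (68% with Fisher). Reaching 80% needs about 49 evaluable per group by the pooled formula.

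These figures rest on the plan's own rates, 1:1 allocation, 38 read as per group, and a comparison of 30-day proportions. The two-sided reading rests on convention, not on the documents. The correction should be required, because this is the protocol's only statistical section and its one power figure depends on a choice that it does not declare.

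**What to change.** Rewrite the sample-size sentence to give 38 evaluable per group (76 in total, 88 enrolled), the allocation ratio, the test, and its sidedness. Then take one of two routes:

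- **Two-sided 5%.** Restate the power for 85% versus 60% as about 70% with 38 evaluable per group, and about 76% if all 88 are evaluable. Alternatively, say that 38 per group has 80% power for about 60% versus 88%. If Fisher's test or a continuity correction will be used, quote the lower power for that test.
- **One-sided 5%.** Declare it in the protocol before the data are analysed, with the reason, and name an uncorrected test if the 80% is to stand.

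Either route costs one or two sentences and changes nothing in the conduct of the trial. The cost of the two-sided route is a less favourable stated power.

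If the sponsor prefers to keep 80% power at two-sided 5% for the original rates, about 98 evaluable subjects are needed. At the implied retention of 76/88, that is 98 × 88/76 = 113.5, or 114 enrolled, which is 26 more than planned. At the plan's own recruitment figures (505/12 × 0.5, about 21 a month), enrolling 114 would take about 5.4 months, against the stated 5 or so.

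### The trial is sized on one day-30 healed/not-healed comparison, names no healing analysis, and has about 69% power at two-sided 0.05; a prespecified all-visit model with baseline wound size may regain some or all of the shortfall.

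*Combined protocol and SAP*

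**What the plan says.** The Biostatistical Analysis section opens with the aim "To detect a 25% difference in time to improvement in each treatment arm with an 80% power". It then gives the basis of the sample size: "This was calculated by considering the percentage of patients that would be healed by 30 days", with "In the timolol group, we estimate 85% and in the control group we estimate 60" per cent. The figure is 38 at alpha 0.05, and "Total subject enrollment will be 88 to adjust for subjects lost to attrition". Sidedness, test, model, covariates and handling of missed visits are not stated there or anywhere else.

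The healing aim under Specific Aims is reduction in wound surface area. Under Study Procedures (end of the SOC group text), "Patients will be followed up at 7, 15, and 30 days", and again at 3 and 6 months. A blinded physician assesses wound area by planimetry on photographs at each follow-up visit. No day-0 photograph or area is listed, although starting size is needed for the eligibility limit (Subject Selection), for application by wound area (Case group) and for any measure of area reduction.

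**The concern.** Three descriptions of the healing effect sit side by side: time to improvement, area reduction, and percentage healed at day 30. Only the last has planning figures. As a comparison it scores closure by day 7 the same as closure on day 29, ignores what happens between day 30 and month 3, and does not use starting size. Potential Benefits names quicker healing as the first expected gain, and a single day-30 proportion answers that only in part.

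Two things are at stake. If the final test is two-sided, as is usual, the trial is about 11 points short of its stated power. And with no analysis named, the choice among several reasonable ones could be made after the data are seen.

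**Working it through.** **Inputs.** Healed by day 30: p1 = 0.85, p2 = 0.60; alpha 0.05, sidedness not stated; power 80% (all Biostatistical Analysis). I read 38 as per arm: 88 enrolled is 44 per arm under 1:1 allocation, and 88 − 76 = 12, or 13.6%, is left for attrition. The 1:1 ratio is an assumption; Study Procedures says only "Eligible subjects will be assigned by computer-based randomization to case (0.25% timolol gel) or control (SOC) group". Month 3 is taken as day 90.

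**1. Reproducing 38.** n per arm = [z_α√(2p̄q̄) + z_β√(p1q1 + p2q2)]² / (p1 − p2)², with p̄ = 0.725, √(2p̄q̄) = √0.39875 = 0.6315 and √(p1q1 + p2q2) = √0.3675 = 0.6062.
- One-sided: (1.645 × 0.6315 + 0.842 × 0.6062)² / 0.0625 = 38.4, so 39. The arcsine formula gives 37.5, so 38.
- Two-sided: (1.960 × 0.6315 + 0.842 × 0.6062)² / 0.0625 = 48.9, so 49. The arcsine formula gives 48, and the continuity-corrected formula 57.

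The plan's 38 is reproduced only with one-sided 0.05.

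**2. Power of the day-30 comparison.** Power = Φ{[0.25√n − z_α × 0.6315] / 0.6062}.
- n = 38, two-sided: (1.541 − 1.238)/0.6062 = 0.50, giving 69.2%.
- n = 38, one-sided: (1.541 − 1.039)/0.6062 = 0.83, giving 79.6%.
- n = 44 (no attrition), two-sided: (1.658 − 1.238)/0.6062 = 0.69, giving 75.6%.

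**3. What healing times could carry.** Under proportional hazards the same rates imply HR = ln(0.15)/ln(0.40) = 2.07. Events for 80% power, two-sided: 4(1.960 + 0.842)²/(ln 2.07)² = 59.3, so 60. With 76 patients, about 73-76 would heal by day 90, giving 88-89% power if healing times were known exactly. Four visits give less.

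**4. Four visits, simulated.** 38 per arm, two-sided 0.05, calibrated to 60% vs 85% at day 30, healing known only at days 7, 15, 30 and 90, no attrition among the 38. Model: grouped-time complementary log-log. There were 1,500 runs per Weibull scenario and 1,000 per log-normal scenario, so Monte Carlo error is about 1 point. Power in %:

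| Assumed healing times | Day-30 chi-square | All visits, no size | All visits + size, size not prognostic | All visits + size, size moderately prognostic |
|---|---|---|---|---|
| Weibull, shape 1 | 70 | 84 | 82 | 92 |
| Weibull, shape 1.5 | 71 | 78 | 77 | 89 |
| Weibull, shape 2 | 71 | 74 | 74 | 86 |
| Weibull, shape 3 | 71 | 75 | 74 | 82 |
| Log-normal, log-SD 0.4-0.9 | 68-74 | 81-87 | 82-86 | 87-97 |

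Moderately prognostic means a log hazard ratio of 0.5 per SD of size (Weibull), or size explaining 20-40% of the variance in log healing time (log-normal). A day-30 logistic model with size reaches 76-77% at the same Weibull setting, so part of the gain comes from size alone.

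**5. A late effect.** If the arms differ only between days 15 and 30, and 96-100% are healed in both by day 90, the all-visit model with size (here not prognostic) has 43-66% power, against 71-72% for the day-30 chi-square.

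**6. Type I error.** Likelihood-ratio tests rejected in 5.1-5.8% of null trials. Wald tests rejected in 5.7% unadjusted and 6.7% adjusted.

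**The case against.** A reader might infer that the protocol commits to a single day-30 yes/no analysis that discards later visits and drops anyone who misses day 30. The documents do not support that. The day-30 percentage appears only as the basis of the sample size, and no analysis or missing-data rule is written. Those losses belong to the sizing comparison if it were carried over unchanged.

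A reader might also infer that power is plainly missing and that using all visits restores it at no cost. None of the three parts stands without conditions. The shortfall exists only under a two-sided test; read as one-sided, 38 per arm gives the stated power. Restoration is not general: with rising hazards and size not prognostic, power stays at 74-77%, and with a late effect it falls below the day-30 test. Most of these small wounds may be closed in both arms by month 3, so convergence cannot be dismissed. Nor is it free, because the covariate behind the higher figures is a day-0 area that is not among the listed measurements.

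It is also fair to say that a day-30 analysis adjusted for size is a respectable alternative. What remains is that the plan must name an analysis, and that the one its own wording (time) and visit schedule point to is usually the more powerful.

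**Conclusion.** The point holds in conditional form. The sizing rests on one day-30 proportion, the effect is described as a time difference, and no analysis is specified. At two-sided 0.05 the sizing comparison has 69% power with 38 per arm, and 76% even if all 44 per arm are kept.

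A prespecified all-visit model may regain some or all of the shortfall: about 74-87% without size, and 82-97% if size is moderately prognostic, when the effect acts throughout healing. These ranges rest on assumptions that are not in the documents: 1:1 allocation, Weibull or log-normal healing times, the prognostic strength of size, and month 3 as day 90. The eligibility limit on wound size also narrows the range of the covariate. The arithmetic on the day-30 comparison rests only on the plan's own figures, the per-arm reading of 38 and the sidedness.

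**What to change.** Add one paragraph to Biostatistical Analysis stating that:
- healing is analysed in all randomised patients, two-sided at 0.05, as interval-censored time to the first visit with zero planimetric area (days 7, 15, 30 and month 3);
- the model is a grouped-time complementary log-log model with treatment, visit interval and log baseline wound area, tested by likelihood ratio or permutation rather than by a Wald test;
- observed healing carries forward, and a missed visit widens the interval instead of removing the patient;
- the difference in percentage healed by day 30, adjusted for baseline area, is reported alongside with its 95% CI.

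Add a standardised day-0 photograph and planimetric area to Study Procedures.

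Cost: a paragraph, some programming and one photograph per patient, with no extra visits or patients. The effect measure becomes a hazard ratio that assumes proportional hazards. If the sponsor expects a late effect with convergence by month 3, this test has less power than the day-30 comparison; that judgement should be made and recorded before outcome data by arm are seen.
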